**Accuracy of complete-arch digital implant impression with newly
designed scan bodies.**

2020/10/10

Accuracy of complete-arch digital implant impression with newly designed scan bodies.

Objective

To investigate the accuracy of complete-arch digital implant impression using newly designed scan bodies.

Inclusion Criteria:

At least 18 years old and able to understand an informed consent

Fully edentulous jaw

2-6 dental implants have been placed in the edentulous jaw

The implants have been osseointegrated

Mouth opening larger than 4.5 cm

Exclusion Criteria:

Poor oral hygiene

Presence of peri-implantitis or peri-implant mucositis

Presence of temporomandibular joint disease

Unwilling to participate in the research

Study design

(1) Test data: for each patient, the follow three impressions are made.

- ① Conventional splinted open-tray impression:** A preliminary stone cast are produced using alginate impression material. Impression copings are connected to the implant analogs and splinted with self-cured pattern resin. The splinted assemblies are cut and connected to the abutments intraorally, and then reconnected. Open-tray impressions are made using siloxane impression material. The stone casts are poured with low expansion type IV gypsum. Scan bodies without extensional structure are connected to the analogs fixed in the stone casts, which are then digitalized with a laboratory scanner. The digital models are exported as STL files.
- ② Digital impression using scan bodies without extensional structure:** scan bodies without extensional structure are connected to the abutment intraorally and scanned with an intraoral scanner. The digital models are exported as STL files.
- ③ Digital impression using scan bodies with extensional structure:** scan bodies with extensional structure are connected to the abutment intraorally and scanned with an intraoral scanner. The digital models are exported as STL files.

(2) Reference data

The scan bodies with extensional structure are connected with self-cured pattern resin intraorally. The splinted scan bodies are scanned with a laboratory scanner and exported as STL files.

(3) Data analysis

The STL files are imported to an inspection software. Each of the test data is aligned

with the reference data using “best-fit” algorithm. The deviations between test data and reference data are calculated automatically.

(4) Statistics

Differences between groups in trueness and precision are evaluated using two-way ANOVA, Post-hoc analysis is performed with Bonferroni test. The level of significance was set at $\alpha = .05$.

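### The reference shares its scan-body design with impression 3 only, and the best-fit rule is not restricted to geometry common to all files, so 3 vs 1 and 3 vs 2 can mix shape with accuracy

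*Protocol*

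**What the plan says.** The Objective is "To investigate the accuracy of complete-arch digital implant impression using newly designed scan bodies". Under Study design (1), "for each patient, the follow three impressions are made":

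- Impression 1 (conventional, open tray): "Scan bodies without extensional structure are connected to the analogs fixed in the stone casts", and the cast is then digitised on a laboratory scanner.
- Impression 2: "scan bodies without extensional structure are connected to the abutment intraorally and scanned with an intraoral scanner".
- Impression 3: "scan bodies with extensional structure are connected to the abutment intraorally and scanned with an intraoral scanner".

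Under (2), the reference is built from the extended scan bodies, splinted in the mouth with pattern resin and then scanned in the laboratory.

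Under (3), the measurement rule reads "The STL files are imported to an inspection software. Each of the test data is aligned" "with the reference data using “best-fit” algorithm", followed by "The deviations between test data and reference data are calculated automatically". That is the whole rule. Under (4), trueness and precision are compared between groups by two-way ANOVA with Bonferroni post-hoc tests.

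**The concern.** A best-fit alignment and a surface deviation respond to whatever surface is in the two files. If one file has an extension on each scan body and the other does not, the difference in shape can enter both the alignment and the deviation, even when both files place the implants equally well. Here the file that matches the reference in design is the one made with the new device, and the two comparators do not match it.

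The comparisons at stake are the ones that answer the Objective. A trueness difference between impression 3 and either comparator could come from implant position, from scan-body shape, or from both. A shape effect of this kind is systematic, so enrolling more patients would not average it out.

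**Working it through.** The protocol states no figure on this point, so there is none to reproduce. The check sets the described objects side by side and counts the contrasts.

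**Step 1. What each file contains** (Study design (1) and (2)):

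| File | Scan body | Resin described on the scanned scan bodies | Scanner |
|---|---|---|---|
| Impression 1 | without extension | no | laboratory |
| Impression 2 | without extension | no | intraoral |
| Impression 3 | with extension | no | intraoral |
| Reference | with extension | yes | laboratory |

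Resin is also used in impression 1, but there it splints the impression copings. The scan bodies are attached to the cast afterwards.

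**Step 2. Mismatch of each test file with the reference:**

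- Impression 1: scan-body shape and resin.
- Impression 2: scan-body shape and resin.
- Impression 3: resin only.

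**Step 3. Effect on the contrasts.** Write the measured deviation of impression k schematically as D(k) = A(k) + S(k) + R(k), where A is true inaccuracy, S the contribution of the extension mismatch and R that of the resin. Surface deviations are not strictly additive; the notation only tracks what enters.

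- D(3) − D(1) contains A(3) − A(1) and S(3) − S(1). Impression 3 has no extension mismatch and impression 1 has one, so the shape terms need not cancel.
- D(3) − D(2) contains A(3) − A(2) and S(3) − S(2), with the same consequence.
- D(1) − D(2) compares two files with the same scan-body type, so the extension does not distinguish them.
- R is present for all three files. It may add error, and perhaps unequally, but nothing in the document makes it clearly different between impressions.

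**Step 4. Count.** Pairs among three impressions: 3 × 2 / 2 = 3. Pairs involving the new design: 2 (3 vs 1, 3 vs 2), both across unlike shapes. Pairs of like shape: 1 (1 vs 2), which does not test the new design. This assumes that the post-hoc tests cover all pairs, which the protocol does not list.

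**Step 5. Does the written rule remove S?** It would if alignment and measurement used only geometry present in every file, or if each scan body were converted to an implant position and axis. Neither step is written.

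**Step 6. Size.** A value for S needs the dimensions of both scan bodies, the compared region and the direction of measurement (test to reference, or the reverse). The document gives none of these, so neither size nor sign can be calculated. Nor can the effect on precision be judged, because the document does not define precision.

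**The case against.** The strongest reply is that this is operational detail. Selecting a region and trimming files are routine in inspection software and may be set out in an analysis plan that is not at hand. The protocol never says that whole surfaces, extensions or resin are fitted, and its wording is compatible with a comparison limited to a shared region. Since the two designs are named only by the presence or absence of an extension, they may well have a common core. If the comparison is limited to such a core, the shape effect falls away.

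Much of this stands, and it is why the point is conditional. It does not dispose of it. The protocol has its own Data analysis section that fixes the measurement procedure, and that procedure, taken literally, does not suit the objects described just before it. If a restriction is already used in practice, the correction is simply to write it down.

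Two further replies are right. Resin should not be presented as a confounder peculiar to 3 vs 1 and 3 vs 2, because no test file is described as carrying it. And counts of contrasts show where a bias could act, not that one exists.

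A reader might also infer that the design favours the new scan body, because the reference was made with it. The document does not support a direction. That would require the dimensions, compared region and direction of deviation that are not given, and any simulated value would rest on invented geometry.

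**Conclusion.** The point holds in conditional form. The reference shares its scan-body design with impression 3 alone, and the stated rule does not confine alignment or measurement to common geometry. If it is applied to the files as exported, trueness in 3 vs 1 and 3 vs 2 mixes scan-body shape with accuracy; 1 vs 2 is free of the extension effect. The reach is 2 of 3 pairwise contrasts, both of those bearing on the Objective. Magnitude and direction are undetermined.

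The conclusion rests on two assumptions: that no unwritten cropping or library step is applied, and that all pairs are compared. It does not show that the trueness results will be wrong. It is worth correcting before the files are analysed, because the contrasts affected are the ones the study is for and the remedy is modest.

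**What to change.** Amend Data analysis to require that, before both alignment and deviation measurement, every test and reference STL is cropped to the resin-free scan-body portion that both designs share. Extension, resin, mucosa and gypsum are excluded, and the same direction of deviation is used in all groups. The sponsor must first confirm that such a portion exists.

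Alternatively, where library files of both designs with a shared platform datum exist, register each scan body in every file to its own library file, reduce it to platform centre and axis, and compare inter-implant distances and axis angles with the reference. With n implants there are n(n − 1)/2 distances and as many angles: 1, 3, 6, 10 and 15 for n = 2 to 6, the range allowed by the Inclusion Criteria. The protocol mentions no library files, so this route cannot be taken as available, and it changes the outcome from a surface deviation to distances and angles.

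A sentence acknowledging the limitation would be accurate but would not repair the two contrasts.

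Cost: protocol wording and extra software work per file on STLs already exported, with no added patients or procedures. Cropping leaves less surface for the best fit. Library registration adds a small error, possibly different between designs, which should be reported.
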